The study is a prospective, single centre, double-blinded randomized controlled trial whose **goal** is to compare the immune response of a population of immunosuppressed pediatric patients with autoimmune diseases on immunosuppressive medications to two different doses of Hepatitis A vaccine. The objectives are (a) to confirm that adolescents, like their adult counterparts, have a reduced immune response to hepatitis A vaccine, and (b) to compare the immunogenicity of two different dosing options of vaccine for this age group after one and two doses. A total of 60 adolescents aged 12 – 15 years with confirmed autoimmune disease for which they are being treated with an immunosuppressive therapy will be recruited from the Rheumatology and Gastroenterology Clinic at Alberta Children's Hospital (ACH). Those found to have no immunity to hepatitis A will be enrolled. Informed, written consent will be obtained from the parent or guardian of subject, with assent obtained from the study subjects. Subjects will be randomly assigned to two doses of either Avaxim Pediatric® or Avaxim ® (adult) vaccine (Sanofi Pasteur Canada), six months apart, with hepatitis A titres done at baseline and one month after each dose. Both formulations are licensed for this age group.

1. INTRODUCTION

A variety of childhood autoimmune diseases such as granulomatosis with polyangiitis, juvenile idiopathic arthritis, inflammatory bowel disease or systemic lupus erythematosus are now controlled using immunosuppressive medications. These commonly include biologics such as tumor necrosis factor-, interleukin 1 or 6 - antagonists along with disease-modifying anti-rheumatic drugs (DMARDs) such as methotrexate. Disease control comes at the risk of increased infection. Many important childhood infections can be prevented with effective vaccines, most of which are administered early in life. For vaccines that can be safely given while on immunosuppressive medication, a blunted and/or rapidly waning immune response may occur. This has been demonstrated for several routine vaccines, but there is virtually no such data available for prevention of travel-related diseases in immunocompromised children.

Hepatitis A vaccine is given as 2 doses; in healthy pediatric hosts, 97-100% will have a protective response a month after the first dose, therefore they are protected for an imminent trip without completing the 2-dose series. Similar results are documented for all inactivated hepatitis A vaccines, which can be used interchangeably. The second dose is given in 6-12 months to ensure lasting protection. In adults with drug-induced immunosuppression, there are recent publications reporting significantly reduced responses to hepatitis A vaccine. An open label study in adults with rheumatoid arthritis on tumor necrosis factor-inhibitors and / or methotrexate, only 10% had an adequate immune response one month after the first dose. This rose to 83% a month after the second dose. This confirms the deleterious impact of immunosuppressive medications on response to this vaccine, most dramatically so in those on increasingly suppressive regimens. The increase in protective rates after the second dose suggests that given sufficient exposure to antigens in the vaccine, these individuals could mount a much better response. However it is unrealistic for most people to plan and prepare for their trips so far in advance, therefore it would be ideal to find a way of protecting immunosuppressed persons more rapidly, in other words after the first dose. An increased dose of vaccine has been shown to be successful in eliciting a protective immune response to hepatitis B in immunocompromised hosts, such as those on dialysis. There has been success with use of double-dose hepatitis A and B vaccines in such populations (personal communication – [name]).

Bringing these various considerations together, a pilot study of vaccine responsiveness of adolescents on immunosuppressive medications for autoimmune diseases to 2 different doses of Hepatitis A vaccine

will confirm the suboptimal response to this important travel vaccine in a pediatric immunocompromised population, and explore one means of improving it.

2. OBJECTIVES

The objectives of this study of adolescents aged 12 – 15 years with autoimmune diseases treated with immunosuppressive medication are:

1. To confirm whether this population has a reduced immune response to pediatric Hepatitis A vaccine compared to published data on immunocompetent adolescents; and
2. To compare the immunogenicity of 2 formulations of Hepatitis A Vaccine (pediatric and adult) after the first and second doses

3. STUDY DESIGN

This is a prospective, single centre, randomized, controlled trial comparing immune responses to two doses of a licensed Hepatitis A vaccine in children. Subjects will receive 2 doses (0.5 mL each) of the assigned study vaccine (Avaxim Pediatric® or Avaxim ® (adult) vaccine). One lot of each vaccine formulation will be studied. All subjects will provide safety observations using a diary and sequential blood samples will be obtained to measure serologic/immunologic responses.

4. STUDY PARTICIPANTS

4.1 Population/number of subjects

The study population will include 60 subjects, males and females, in the age range 12 – 15 years. The maximum age at enrollment is 15 years and 5 months, to allow for up to 7 months in which to complete 2 doses of vaccine before age 16 years.

4.2 Study center

This pilot will be conducted at the Alberta Children's Hospital site, with patients recruited through the ACH Rheumatology and Gastroenterology Clinics.

4.3 Inclusion criteria

Subjects must meet all of the following inclusion criteria and none of the exclusion criteria to participate in this study.

Criteria that apply to all subjects include:

- Written informed consent provided for the subject by a parent or legal guardian.
- Written informed assent from the participants themselves.

- Subjects whose parents the investigator believes can and will comply with the requirements of the protocol (i.e. return for follow-up visits, record safety observations, able to converse with study personnel and contactable by telephone).
- Age 12 years to 15 years and 5 months
- Confirmed autoimmune disease
- Maintained on any immunosuppressive medication with the exception of pulse steroids

4.4 **Exclusion criteria**

The following criteria apply:

- Systemic hypersensitivity to any Hepatitis A vaccine component such as neomycin, 2-phenoxyethanol, formaldehyde, aluminum hydroxide, Medium 199 Hanks, or Polysorbate 80.
- Thrombocytopenia or any bleeding disorder that contraindicates IM injection or blood collection.
- Receipt of blood or any blood-derived products (including IVIG) within the past 3 months.
- Previous laboratory-confirmed infection with Hepatitis A
- Previous vaccination with any Hepatitis A vaccine

The following conditions are **temporary or self-limiting exclusions** so a subject can be vaccinated once the condition has resolved and no other exclusion criteria exist:

- Current febrile illness or oral temperature of $\geq 38.5^{\circ}\text{C}$ (or equivalent by other route) or other moderate to severe illness within 24 hours before study vaccine administration
- Receipt of any Hepatitis B vaccine within 28 days of planned study vaccine doses. When Twinrix® has been studied, the response to Hepatitis B is amplified by the presence of Hepatitis A. It is unknown whether the reverse is also true.
- Routine childhood vaccines (except MMR and Varicella) must be separated from a study vaccination by at least 7 days.

4.5 **Contraindications to subsequent blood draw**

- Receipt of blood or blood-derived products
- New bleeding disorder that begins after Visit 1
- Receipt of non-study Hepatitis A vaccine

4.6 **Contraindications to subsequent immunization**

- Severe reaction to study Hepatitis A vaccine
- New bleeding disorder that contraindicates IM injection or blood collection.

- Receipt of blood or any blood-derived products.
- Receipt of non-study Hepatitis A vaccine

4.7 **Deviations**

Subjects may be retained in the study in the following circumstances but will be flagged as having deviated from the protocol:

- Serial blood samples provided but one or more beyond the accepted 7 day window
- Blood sample not obtained
- Vaccine administration outside protocol parameters (wrong formulation, dosage etc)
- Vaccine or blood samples stored outside cold-chain parameters

5. CONDUCT OF STUDY

5.1 **Ethics and regulatory**

5.1.1 **Informed consent**

Each authorized representative of a child subject must participate in the informed consent process and sign and date the informed consent form before any procedures specified in this protocol are performed. Given that all subjects are adolescents, informed assent will also be required.

The informed consent discussion, the informed consent and assent forms, and letter of information will include explanations of the following:

- a) That the study involves research
- b) The purpose of the study
- c) The study treatment(s)
- d) The study procedures to be followed, including all invasive procedures
- e) The subject's responsibilities (or those of the subject's representative in the case of children)
- f) The aspects of the study, that are experimental
- g) The reasonably foreseeable risks or inconveniences to the subject
- h) The reasonably expected benefits. When there is no intended clinical benefit to the subject, the subject should be made aware of this
- i) The alternative procedure(s) or course(s) of treatment that may be available to the

subject, and their important potential benefits and risks

- j) The compensation and/or treatment available to the subject in the event of trial-related injury
- k) The anticipated pro-rated payment, if any, to the subject for participating in the trial
- l) The anticipated expenses, if any, to the subject for participating in the trial
- m) That the subject's participation in the trial is voluntary and that the subject may refuse to participate or withdraw from the trial at any time, without penalty or loss of benefits to which the subject is otherwise entitled
- n) That any REB will be granted direct access to the subject's original medical (study) records for verification of clinical trial procedures and/or data, without violating the confidentiality of the subject, to the extent permitted by applicable laws and regulations and that, by signing a written informed consent form, the subject or the subject's legally acceptable representative is authorizing such access
- o) That records identifying the subject will be kept confidential and, to the extent permitted by applicable laws and/or regulations, will not be made publicly available. If the results of the trial are published, the subject's identity will remain confidential
- p) That the subject or the subject's legally acceptable representative will be informed in a timely manner if information becomes available that may be relevant to the subject's willingness to continue participation in the trial
- q) The person(s) to contact for further information regarding the trial and the rights of trial subjects, and whom to contact in the event of trial-related injury
- r) The foreseeable circumstances and/or reasons under which the subject's participation in the trial may be terminated
- s) The expected duration of the subject's participation in the trial
- t) The approximate number of subjects involved in the trial

5.1.2 Regulatory considerations

Both vaccine formulations used in this trial has been licensed for use in Canada in the age range of the subjects being studied.

5.1.3 Monitoring

Investigators will be made aware of any concerns with respect to vaccine reactions or changes to the stability of the underlying disease condition of the subject(s).

5.2 Outline of study procedures

5.2.1 Study outline

		Vaccine Dose #1		Vaccine Dose #2	
Activity	Screening (Visit 0)	Day 0 (Visit 1)	Day 28 (Visit 2)	Day 0 (Visit 3)	Day 28 (Visit 4)
Window		+7 days		+7 days	
Recruitment	X				
Informed consent	X	X (can be done in advance)			
Eligibility review		X	X	X	X
Health assessment		X	X	X	X
Blood Sample	X	X	X	X	X
Randomization, Group A or B		X			
Vaccination		X		X	
Safety review			X		X
Safety monitoring instruction		X	X	X	X

5.2.2 Randomization Process

Subject group assignment will be determined following enrolment and eligibility confirmation by sealed envelope to be opened by the unblinded vaccination nurse. A randomly-generated list will assign study vaccine group by subject study number, and maintained by an unblinded Study Staff member. Given the narrow age range of subjects, they will not be stratified by age.

- Review contraindications to subsequent immunization and blood sample collection

- Collect blood sample (10-30 mL) from all subjects.
- Administer dose 2 of Hepatitis A vaccine (same type as dose #1).
- Observe subject for 15 minutes with appropriate medical treatment readily available in case of emergency
- Instruct the parent to contact the investigator promptly to report any serious adverse event (SAE) occurring during the subsequent 28 days
- Instruct the parent to record daily any symptoms or signs of illness in a provided diary.

Visit 4 (28-35 days after Visit 3)

- Confirm parent's ongoing consent to subject's participation
- Review parent's safety and health observations for subject for days 1-28 following vaccination, including the diary. If the safety review is delayed beyond day 28, it should remain focused on observations for days 7 to 28.
- Report any AEFI provincially as required, with a de-identified copy to VSS at PHAC and to the PCIRN Manager. If the AEFI is an SAE ensure that it is provided to PHAC within 24 hours of being reported
- Review contraindications to subsequent blood sample collection
- Collect blood sample (10-30 mL) from all subjects.
- Obtain consent from subject's parent/guardian to participate in future trials eg to assess duration of protection after vaccination.

5.2.4 Non-study vaccines

Hepatitis B vaccinations should not be given while subjects are participating in the study as they could interfere with evaluation of the study vaccines. Subjects can receive any other routine childhood vaccines during the study if essential, provided those vaccinations are separated from a study vaccination by at least 7 days. Non-study Hepatitis A vaccines cannot be given.

5.2.5 Health assessments

A health history will be reviewed at Visit 1 to confirm an autoimmune disease for which the subject is receiving immunosuppressive medications (except for pulse steroids); additional pre-existing conditions including whether or not any prescription medications are being taken for the condition will be noted (no medication details will be collected). The health assessment will be sufficiently detailed to confirm eligibility to participate (subject has no medical exclusions) and to identify a baseline for appropriate assessment and management of any reportable AEFIs. Height and weight measurements will be noted at enrolment.

5.2.6 Data collection

Data will be collected using source documentation and will be transferred as applicable to the electronic equivalent of a case report form. A secure, PC-based database program will be used to enter data.

The following data elements will be collected (along with safety data described in section 7.0):

Demographics: date of birth, gender.

Autoimmune condition: autoimmune disease, disease activity status, immunosuppressive medication.

History of Hepatitis A vaccination(s): lack of prior vaccination will be confirmed.

Height and weight, obtained at Visit 1. These measurements will be used to calculate BMI.

Protocol compliance: consent date and time, visit dates; immunization details (protocol adherence regarding administration and cold chain, product, date, time); blood sample details, vaccine cold chain); completion of safety reviews and dates.

5.3 Laboratory

5.3.1 Sample collection and handling of specimens

Blood (10-30 ml) as a source of serum/plasma will be taken by standard venipuncture and processed according to a standardized operating protocol. All serum/plasma specimens collected will be catalogued using Study Number, processed, aliquoted to limit repeated freeze-thaw cycles and then kept in storage at -80°C at a local lab at the University of Calgary until required for assessment.

5.3.2 Serology testing

Hepatitis A antibodies will be analyzed quantitative in serum using the commercially available immunoassay Elecsys Anti-HAV (Cobas®) according to the manufacturer's protocol (Roche Diagnostics GmbH, Mannheim, Germany). This testing will be performed by [name], Public Health Agency of Canada.

5.3.3 Other tests

Additional testing of the humoral and T-cell immune response in serum and/or plasma will be performed including cytokine profiles and autoantibodies (cross-reactions).

Serum samples will be tested for a spectrum of autoantibodies ([name] lab, Calgary). These assays include a screening indirect immunofluorescence assay on HEp-2 substrate (Inova Diagnostics Inc., San Diego, CA); autoantigen arrays covering a spectrum of over 25 different well-established targets by ALBIA (TheraDiag, Paris, France), line immunoassays (Euroimmun, Lubeck, Germany) and BioFlash CIA (Inova).

Plasma cytokine/chemokine levels will be assessed using customized multiplexed laser bead assays provided by Eve Technologies (Calgary, AB), according to the manufacturer's instructions (For a

complete list of the cytokines/chemokines in the 64-plex array see: <https://www.evetechologies.com/discoveryAssayListHuman.php>).

In patients for whom consent is obtained, samples will be also stored for future immunology studies related to immunization responses.

6. VACCINES AND ADMINISTRATION

6.1 Hepatitis A study vaccines

The HAV vaccines to be used in this study will be produced by Sanofi Pasteur (Toronto, ON). Supplies will be obtained from single , following strict cold chain procedures. Each 0.5 mL dose of Avaxim Pediatric® contains 80 antigen units, while Avaxim® (adult) contains double this amount (160 antigen units). Both vaccines contain the following: excipients 2-phenoxyethanol, formaldehyde, aluminum hydroxide (expressed as aluminum to which HAV is adsorbed), Medium 199 Hanks, and polysorbate 80. Manufacturing process residuals include neomycin.

6.2 Dosage and administration of pandemic vaccines

The dosage to be evaluated is 0.5 mL of either formulation. Two doses will be given, separated by 6 – 7 months.

The procedure for administering AVAXIM® Pediatric or AVAXIM® is as follows: Shake the pre-filled syringe well until a uniform, cloudy suspension results. AVAXIM® Pediatric may be packaged with a choice of two needles. Select a needle of appropriate length to ensure that the vaccine will be delivered intramuscularly; in most adolescents this will be 25mm. Remove the tip cap from the syringe, take the chosen needle from the blister pack and fix to the tip of the pre-filled syringe. If a syringe with attached needle is present, the vaccine is ready to administer.

The vaccine is injected intramuscularly. The deltoid muscle is the preferred site. The non-dominant arm can be selected if preferred. Vaccinators can alternate between sides if desired. Vaccines must not be injected intravascularly. The full recommended dose of vaccine must be used.

6.3 Vaccine Formulation Blinding

Parents/guardians will not be told which study vaccine formulation is administered at the vaccination visits. This information will be provided when the study results are conveyed to parents.

6.4 Storage

Vaccines and adjuvant multi-dose vials should be stored refrigerated at 2° to 8°C, avoiding freezing (ref). Vaccine storage temperature should be monitored and recorded daily.

6.5 Allocation

Vaccine allocation is from the open supply of study vaccines. Documentation of wasted and replaced vaccine is not necessary.

7. VACCINE SAFETY

7.1 Immediate post-vaccination observation for anaphylaxis

Subjects should be observed for at least 15 minutes after the vaccination for any signs or symptoms of anaphylaxis. Research personnel should be equipped to assess such changes and administer appropriate initial medication.

7.2 Observations during days 0-6 post-vaccination

Parents will be asked to make daily notes of any illness symptoms in subjects during the week after vaccination, using a diary supplied for this purpose.

- a) **injection site:** presence or absence of **local and armpit pain or tenderness**, and if present, the maximal severity on that day based on the most appropriate descriptive term as follows:
 - mild: present but doesn't interfere with daily activities or limb motion
 - moderate: interferes with daily activities or limb motion
 - severe: prevents usual daily activities or limb motion
- b) **injection site:** maximum diameter that day of any **redness or swelling, induration (lump)** based on daily measurements using a transparent device (supplied) with concentric circles 1, 2, 3, 4 and 5 cm diameter.
- c) **fever:** daily (maximum) temperature to be measured and recorded each day using an electronic thermometer to be provided. Values $\geq 38.5^{\circ}\text{C}$ (oral or equivalent) will be defined as fever in the analysis. Measurements should be made each evening or whenever subjects feel feverish, with the highest value to be recorded. Either rectal or axillary measurements will be made, depending upon the age and cooperativeness of the child. Measurement site to be noted.
- d) **general symptoms:** shivering, sweating, irritability, drowsiness, sleep disturbance decreased appetite to be noted and rated each day for severity as above.
- e) **other (unsolicited) symptoms that interfered with daily activities** will be recorded, with start/stop dates and maximum severity.
- f) **health impact:** The health impact of post-immunization symptoms will be described using assessment indicators such as requiring a doctor visit, ER visit, hospitalization, newly prescribed medication or change in baseline prescription medications or missed days of school or parent employment resulting from illness of the adolescent. The specific (most bothersome) type of symptom (local or specific systemic complaint) that compelled the parent to seek medical advice or the adolescent to miss school will be identified.

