9.2.1 Safety observations

The 2 vaccines in this study are both licensed for use in the age group of the study population. Reactions will be documented in order to identify potential differences in the rates of local reactions and/or significant health events between groups.

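### Fever is cut at 38.5 °C oral or equivalent, but section 7.2(c) plans only rectal or axillary readings and does not define the equivalence

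*Combined protocol and SAP*

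**What the plan says.** Everything central is in item (c) of section 7.2, which covers the diary for days 0 to 6.

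- **Definition.** A value of 38.5 °C or above ("oral or equivalent) will be defined as fever in the analysis".
- **Device.** The daily maximum is to be "measured and recorded each day using an electronic thermometer to be provided".
- **Site.** "Either rectal or axillary measurements will be made, depending upon the age and cooperativeness of the child".
- **Record.** "Measurement site to be noted".

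Four other places bear on it.

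- Section 4.1 describes the subjects as "males and females, in the age range 12 – 15 years". Section 5.2.2 treats that span as too small to matter for allocation: "Given the narrow age range of subjects, they will not be stratified by age".
- The temporary exclusions in section 4.4 use the same oral threshold with the same open phrase, "or equivalent by other route) or other moderate to severe illness within 24 hours before study vaccine administration", and also give no equivalence.
- Section 7.3 refers back to items (a) to (f) of section 7.2 for days 7 to 28, so the fever item carries over to significant health events in that period.
- Section 9.2.1 states the purpose of the safety data: "Reactions will be documented in order to identify potential differences in the rates of local reactions and/or significant health events between groups".

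**The concern.** The definition and the measurement instruction are parts of the same item and do not fit together. The cut-off is anchored to oral temperature, but neither planned site is oral. Followed as written, every diary temperature counts as fever or not only through the word *equivalent*, which is left undefined for both sites.

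The rule for choosing the site adds to the difficulty. Choice by age and cooperativeness would make sense in a study running from infants to older children. In a group aged 12 to 15 it gives staff and families little to act on, so the mix of sites is likely to be haphazard.

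At stake is whether the reported fever rate can be interpreted and reproduced. One analyst could apply 38.5 °C to the raw readings and another could convert by site first. Nothing in the plan's statistical section settles which, or by how much.

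**Working it through.** The plan gives no figure to reproduce. The check is a comparison of the text, followed by an illustration under a stated assumption.

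**Step 1: the sentences side by side.**

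| Element | Section | Content |
|---|---|---|
| Scale of the cut-off | 7.2(c) | Oral, or equivalent to oral |
| Planned sites | 7.2(c) | Rectal or axillary |
| Basis for choosing the site | 7.2(c) | Age and cooperativeness |
| Age of subjects | 4.1 | 12 to 15 years |
| Site recorded | 7.2(c) | Yes |
| Conversion or site-specific cut-off | 4.4, 7.2(c), 9.1 to 9.2.2 | None |

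The first two rows conflict unless *equivalent* is given a value, and the last row shows that it is not.

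**Step 2: what a raw cut-off would mean.** Let e be the reading at the site minus the oral temperature at the same moment. If 38.5 °C is applied unconverted, a subject is flagged when oral + e ≥ 38.5, that is, when oral ≥ 38.5 − e. The documents give neither the size nor the sign of e for either site, so I assume a size d between 0 and 1.0 °C and show both signs.

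| Assumed d (°C) | Site reads above oral: 38.5 − d | Site reads below oral: 38.5 + d | Gap between two such sites: 2d |
|---|---|---|---|
| 0 | 38.5 | 38.5 | 0 |
| 0.5 | 38.0 | 39.0 | 1.0 |
| 1.0 | 37.5 | 39.5 | 2.0 |

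Where one site reads above oral and the other below, two subjects with the same oral temperature can be classified differently because of the site alone. Section 7.2(c) also keeps only the day's highest value, so if both sites were used on one day the higher-reading one would tend to be kept.

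**Step 3: weight of one subject.** The contribution of one misclassified subject to an arm's fever rate is 1/n.

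- 60 vaccinated, 30 per arm: 1/30 = 3.3 percentage points.
- The 20% immune allowance in section 9.3 taken off the 60: 60 × 0.8 / 2 = 24 per arm, and 1/24 = 4.2 points.
- The 20% drop-out allowance also taken off: 60 × 0.8 × 0.8 / 2 = 19.2, about 19 per arm, and 1/19 = 5.3 points.

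These figures show how sensitive the rate is to a single subject. They do not estimate how many subjects would be misclassified, because the documents give no expected fever frequency and no expected mix of sites.

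**The case against.** The strongest reply is that the definition already admits other routes. It says oral *or equivalent*, so rectal and axillary readings fall within it. A reader might infer that no planned reading can be judged against the definition at all; the text does not support that. The gap is that the equivalence has no stated value, not that such readings are barred.

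Second, the site is recorded. That is the item needed for a conversion or a site-specific cut-off, so the information is not lost. This stands and makes the repair cheap. It does not make the repair unnecessary, since a conversion chosen after the data have been seen is not prespecified.

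Third, a reader might infer that the fever rate is bound to be wrong, or that the comparison of the vaccines is biased. Neither follows. The rate is wrong only if the cut-off is applied unconverted and the true offset is not zero, and applying it raw to every site would itself disregard the equivalence wording. Assignment is randomised (section 5.2.2) and parents are not told the formulation (section 6.3), so the site should not differ systematically by arm. At this sample size the mix could still differ by chance.

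Fourth, the outcomes in section 9.1 are serological. Section 9.2.1 names local reactions and significant health events but neither names fever separately nor plans a test for it. This stands and limits the importance of the point.

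Finally, a reader might infer that families pick the site freely. Section 7.2(c) states the basis for the choice but not who makes it.

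**Conclusion.** The inconsistency in section 7.2(c) is real: the cut-off is tied to oral temperature, the only planned sites are rectal and axillary, the basis for choosing between them does not suit subjects aged 12 to 15, and the equivalence is undefined. The consequence is limited to possible misclassification in the absolute rate of a descriptive safety item. Under an assumed offset of 0 to 1.0 °C in either direction, an unconverted 38.5 °C cut-off acts as an oral cut-off somewhere from 37.5 to 39.5 °C. That range rests wholly on the assumption. The primary and secondary outcomes are untouched, and no systematic bias between arms is expected. It is a minor point, worth correcting because the correction costs almost nothing.

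One reservation: the diary itself is not reproduced in the document, so its instructions may be more specific than section 7.2(c).

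**What to change.** Reconcile the two sentences in section 7.2(c), and the matching diary instruction, so that one measurement site is used for all subjects and agrees with the site to which the cut-off refers. Oral readings would match the cut-off as now written, provided the supplied electronic thermometer allows them; restating the definition for another single site would also remove the conflict. Drop the choice by age and cooperativeness.

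For any reading taken at another recorded site, state one equivalence per site, fixed before database lock, and apply it to both arms alike. This also covers mixed-site readings already collected. The same undefined phrase in section 4.4 should be reconciled with whatever is decided.

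The cost is one sentence in section 7.2(c) and one in the diary, filed with the ethics board as a modification under section 10.1. The design, sample size and primary analysis do not change.
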